## 2.2 Exclusion Criteria

- 2.2.1 Patients with symptomatic leukemic meningitis will be excluded. However, patients that have both ATL and another HTLV-I-associated disease, tropical spastic paraparesis (TSP), will be included.
- 2.2.2 Pregnant and nursing patients are not eligible for the study. Because the effects of Denileukin diftitox on the developing fetus are unknown pregnant women will be excluded. Breast-feeding in patients with HTLV-1 infection is contraindicated because of the risk of transmission of the virus to the child. In addition, Denileukin diftitox may be present in breast milk and produce adverse events in the breast-feeding child.
- 2.2.3 HIV positive patients are excluded from the study. Denileukin diftitox may produce a different pattern of toxicities in immunocompromised individuals.
- 2.2.4 Patients with Smoldering ATL are excluded.
- 2.2.5 Patients with serious intercurrent illnesses, past history of a myocardial infarction within 6 months or severe coronary artery disease
- 2.2.6 Patients who previously received Denileukin diftitox are ineligible.

## 2.3 Research Eligibility Evaluation

- 2.3.1 Complete history and physical examination, with documentation of all measurable or evaluable abnormalities in the chart. Photos of skin lesions are required.
- 2.3.2 Measurable disease of solid lesions such as lymph nodes and skin nodules will be measured and recorded pretherapy as the sum of the products of two greatest perpendicular diameters of all measurable lesions.
- 2.3.3 Blood: CBC including differential white count and platelet enumeration, reticulocyte count, coagulation profile (PT, PTT), BUN, creatinine, electrolytes, calcium, albumin, phosphorus, sodium, potassium, uric acid, total protein, total bilirubin, direct bilirubin, alkaline phosphatase, SGOT, SGPT, LDH, CPK, amylase, glucose, cholesterol, triglyceride, quantitative immunoglobulins, and complement levels (C3, C4 and total).
- 2.3.4 Blood will be tested for antibodies to hepatitis B, hepatitis C, HTLV-I, and HIV by standard ELISA assays. CMV serology and antigenemia will be obtained.
- 2.3.5 Soluble IL-2R $\alpha$  (Tac antigen) levels in the serum will be measured by ELISA.
- 2.3.6 Anti-diphtheria toxin antibodies will be performed in the Immunology Department.
- 2.3.7 Urine: urinalysis will be performed.
- 2.3.8 Serum Pregnancy test in women of child-bearing potential.
- 2.3.9 Imaging studies: Chest x-ray and CT scan or ultrasound of the abdomen.
- 2.3.10 Skin biopsy of clinically suspicious lesions. One to three lesions may be biopsied to confirm the diagnosis of ATL.

- 2.3.11 Electrocardiogram and Echocardiogram (to estimate ejection fraction).
- 2.3.12 Bone marrow aspirate and biopsy will be obtained before treatment.
- 2.3.13 3 cc of EDTA blood (purple top tube) for surface marker studies (FACS analysis) of peripheral blood mononuclear cells is to be sent to [name] ([name], Ph: [name]). Analysis will include quantitation of total T- and B-cells, as well as Tac (IL-2-R $\alpha$ )-expressing T cells/mm^3. Immunofluorescence staining will be performed using CD3, CD4, CD7, CD8, CD20, anti-Dr, anti-CD25 (either anti-Tac or BD CD25), and 7G7/B6 MoAbs, examining T cell subpopulation. Lymph node aspirates for flow cytometry will be obtained at baseline in patients with easily accessed lymph nodes using the same antibody panel as peripheral blood.
- 2.3.14 A standard recall skin test panel for example [tetanus 1:5 dilution 0.1 ml, PPD intermediate strength (5 T.U./0.1 ml) 0.1 ml, Candida albicans 0.1 ml] will be placed ID. The results will be read 48-72 hours later and recorded in the chart by a physician or nurse practitioner.
- 2.3.15 In patients with leukemia the peripheral blood mononuclear cells will be analyzed for HTLV-I integration and for clonal T-cell receptor gene rearrangements by polymerase chain reaction. Blood is to be sent to the Department of Pathology for analysis.
- 2.3.16 Blood drawing for protocol studies will be limited to 450 cc per 6 weeks.
- 2.3.17 Lumbar puncture. Patients with neurologic signs or symptoms (e.g., cranial nerve palsies, leg weakness, and bowel or bladder dysfunction) that are not known to be due to some other diagnosis and that could be indicative of CNS involvement by leukemia will receive a lumbar puncture prior to treatment.
- 2.3.18 All patients will be asked to undergo leukapheresis prior to receiving their first cycle of therapy and at completion of therapy. The sample shall be sent to [name], Lab of Cellular Oncology, for DNA microarray analysis. Patient identifiers will be removed from all specimens, and they will have assigned a unique number and will be labeled with this number. All future processing such as DNA and RNA extraction as well as microarray analysis will refer to this number in order to protect patient privacy. The key linking patient number to identifying patient information will be kept in a secure log with access restricted to the staff of the [name] laboratory, principal investigator and the medically responsible investigator. All specimens will be submitted to [name], [name]. At least 24 hours notice will be provided prior to sending the sample.
- 2.3.19 Studies must be completed within 4 weeks of study entry, excluding HTLV-1 antibody, which will be counted as positive if obtained from previous studies or HIV and hepatitis viral studies if negative in patients recently enrolled in other NIH protocols within 6 months. Documentation of HTLV1 positivity will be accepted from sources outside the NIH due to the 2 week time frame required for completion of testing at the NIH. Complete blood counts and blood chemistry panels will be repeated within three days before study entry.
- 2.3.20 Pathologic Evaluation  
Diagnostic pathologic specimens will be reviewed by the Hematopathology Section, Laboratory of Pathology, NCI or the Hematology Laboratory, CC. For the subset of patients who do not have circulating abnormal cells a lymph node or skin biopsy will be obtained for diagnostic purposes and to evaluate the expression of the CD25 (Tac) on the malignant cells. Patients with suspected skin involvement from ATL should have skin biopsies. All skin or lymph node biopsies should be submitted fresh in saline to the Hematopathology Section. Biopsy specimens will be processed for routine

histopathology as well as immunohistochemistry in frozen sections and/or flow cytometry for expression of CD25 (Tac) and other lymphocyte surface antigens. Lymph node aspirates will be handled as per the standard procedures of the cytology section. Patients who require a lymph node aspirate or skin biopsy for diagnosis will be entered in the Metabolism Branch screening protocol (97-C-0143) to obtain these samples as they are being performed for eligibility assessment.

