## **2 ELIGIBILITY ASSESSMENT AND ENROLLMENT**

### **Eligibility Criteria:**

#### **2.1 Inclusion Criteria**

- 2.1.1 Patients must have serum antibodies directed to HTLV-I.
- 2.1.2 All patients must have a histologically confirmed diagnosis of adult T-cell leukemia/lymphoma and more than 10% of the malignant cells must express CD25.
- 2.1.3 All stages of Tac-expressing adult T cell leukemia except smoldering are eligible: patients with chronic, lymphomatous or acute ATL are eligible. (See appendix 2 for characteristics of patients with the various stages of ATL)
- 2.1.4 Patients must have measurable disease. All patients with greater than 10% abnormal (i.e. TAC homogenous strongly expressing) PBMC in the peripheral blood will be deemed to have measurable disease.
- 2.1.5 The patient must have a granulocyte count of at least  $1000/\text{mm}^3$  and a platelet count of greater than or equal to  $50,000/\text{mm}^3$ .
- 2.1.6 Patients must have a creatinine of less than 2.0 mg/dl.
- 2.1.7 Omission of cytotoxic chemotherapy for ATL for 3 weeks prior to entry into the trial is required. However, patients receiving corticosteroids will be eligible.
- 2.1.8 Patients must have a life expectancy of greater than 2 months.
- 2.1.9 Eligible patients must be  $\geq 18$  years old. There is no upper age limit.

- 2.1.10 Patients must have SGOT and SGPT value  $\leq 2.5$  times the upper limit of normal and bilirubin  $\leq 3.0$ /dl. If a liver function test is judged to be elevated due to the underlying ATL, this parameter will be considered an unevaluable parameter for toxicity determinations.
- 2.1.11 Patients must have a serum albumin  $\geq 2.5$  g/dl
- 2.1.12 Patients must be able to understand and sign an Informed Consent form.
- 2.1.13 All patients must use adequate contraception during participation in this trial and for three months after completing therapy.

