## **2.4 Patient Registration**

All patients must be registered on study before beginning therapy. To register a patient for the study, contact [name] [contact]), [name] [contact]), [name] [contact]) or one of the other Associate Investigators.

Authorized staff must register an eligible candidate with NCI Central Registration Office (CRO) within 24 hours of signing consent. A registration Eligibility Checklist from the web site (<http://camp.nci.nih.gov/ccr/welcome.htm>) must be completed and faxed to [contact]. After confirmation of eligibility at Central Registration Office, CRO staff will call pharmacy to advise them of the acceptance of the patient on the protocol prior to the release of any investigational agents. Verification of Registration will be forwarded electronically via e-mail to the research team. A recorder is available during non-working hours.

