**Infrequent Serious Adverse Events** - The following serious adverse events occurred at an incidence of less than 5%: pancreatitis, acute renal insufficiency, microscopic hematuria, hyperthyroidism and hypothyroidism. Occasional patients experienced tumor lysis syndrome; patients at risk should receive appropriate prophylaxis prior to administration.

**Pregnancy:** Animal reproduction studies have not been conducted with denileukin diftitox. It is also not known whether denileukin diftitox can cause fetal harm when administered to a pregnant woman or affect reproductive capacity.

**Nursing Mothers:** It is not known whether this drug is excreted in human milk. Because many drugs are excreted in human milk, and because of the potential for serious adverse reactions in nursing infants, patients receiving denileukin diftitox should discontinue nursing.

**Cautions:** Women of child-bearing age and fertile men should be advised to use adequate and effective contraception during treatment with Denileukin diftitox and for at least six months after therapy. The effects of Denileukin diftitox on embryogenesis, reproduction, and spermatogenesis are unknown.

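### The required serum pregnancy test may be four weeks old at study entry, and the readable text does not ensure that pregnancy status is known when dosing starts

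*Combined protocol and SAP*

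**What the plan says.** All references are to the combined protocol and SAP.

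- **Exclusion, 2.2.2:** "Pregnant and nursing patients are not eligible for the study". The reason given is that effects on the fetus are not known. Section 10.1.6 adds: "Animal reproduction studies have not been conducted with denileukin diftitox".
- **Test, 2.3.8:** "Serum Pregnancy test in women of child-bearing potential". No timing is attached to this item.
- **Window, 2.3.19:** "Studies must be completed within 4 weeks of study entry". The only exceptions are the HTLV-1 antibody and negative HIV and hepatitis results from patients recently on other NIH protocols. The pregnancy test is not excepted.
- **Repeat, 2.3.19:** "Complete blood counts and blood chemistry panels will be repeated within three days before study entry". Nothing else is on the repeat list.
- **Entry to treatment, 2.4:** "All patients must be registered on study before beginning therapy". This fixes the order of the two events but not the time between them.
- **Contraception, 2.1.13:** "All patients must use adequate contraception during participation in this trial and for three months after completing therapy".

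**The concern.** A screening window suits a characteristic that is unlikely to change while the window is open. Section 2.3.19 recognises that some results do change, since it asks for counts and chemistry again just before entry. Pregnancy status can also change within four weeks, and it is an absolute exclusion, yet its test stays on the long window.

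A woman could have a negative test at the start of the window and then conceive, or her pregnancy could have been too early to show on that test. In either case she could start treatment with every test-timing rule satisfied, although she does not meet 2.2.2. What is at stake is fetal exposure to an agent whose reproductive effects the protocol itself calls unknown.

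This is a question of participant safety and eligibility. It does not touch the two-stage design, the response endpoint or the toxicity stopping rule.

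**Working it through.** The plan states no figure for the age of the pregnancy test, so there is nothing to reproduce. The check compares the two windows in 2.3.19 and then follows the patient to first dose.

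**Inputs**
- General screening window: 4 weeks = 4 × 7 = 28 days (2.3.19).
- Repeat window for counts and chemistry: 3 days (2.3.19).
- Time from study entry to first dose: *d* days, with no maximum stated (2.4).
- Schedule tolerance: 7 days (Appendix 1 footnote). The documents do not say whether it also extends the screening window.

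**Step 1. Which window applies?** Item 2.3.8 has no timing of its own, and the pregnancy test is not among the exceptions in 2.3.19. The 28-day window applies.

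**Step 2. Oldest result allowed at entry**

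| Test | Oldest result at entry |
|---|---|
| Counts and chemistry | 3 days |
| Serum pregnancy test | 28 days |
| Difference | 28 − 3 = 25 days |

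If the 7-day tolerance is assumed to apply to screening too, the pregnancy test could be 28 + 7 = 35 days old.

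**Step 3. Age at first dose.** The maximum is 28 + *d* days. Study entry is not defined. If it is taken to be the day of first dose, *d* = 0 and the maximum is 28. If it is taken to be registration, *d* has no stated limit and the maximum exceeds 28 by that interval.

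**Step 4. Is a later test scheduled?** No later pregnancy test is required anywhere in the readable text. The Appendix 1 grid has no pregnancy row at screening or on any treatment day, although it draws counts and chemistry on cycle 1 day 1. This is weak evidence: the same grid also has no row for the ECG or echocardiogram, which 2.3.11 requires, and it does not show the 2.3.8 test itself. The Appendix 2 grid could not be read in the copy reviewed. The footnotes that accompany it, including the one on the echocardiogram, do not mention a pregnancy test.

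**Step 5. Does the contraception rule close the gap?** As worded, 2.1.13 covers participation and the three months after therapy. It does not say that it reaches back over the screening period. It also lowers the chance of pregnancy without establishing status, which is what a test does.

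**Step 6. A related contradiction.** Section 2.1.13 sets the post-therapy contraception period at three months. The cautions in 10.1.6 set it at a minimum of six months. The two statements do not agree.

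**The case against.** The strongest reply is that several safeguards act together. Section 2.2.2 is unconditional, so knowingly dosing a pregnant patient would breach the protocol whatever the age of the test. Section 2.4 requires an eligibility checklist and confirmation by the Central Registration Office before drug is released. Section 2.1.13 requires contraception, and nothing prevents an investigator from retesting. The documents set no standard that a four-week window violates, and the three-day figure belongs to tests that serve other eligibility thresholds. In addition, 28 days is an outer limit; the usual timing is not given.

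Much of this stands. A reader might infer that the screening test is the only one in the plan, or that the pregnancy exclusion cannot be enforced. The documents support neither. The first cannot be shown while the Appendix 2 grid is unread, and the silence of Appendix 1 proves little. The second overlooks 2.2.2, 2.1.13 and the registration check.

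What does not fall away is the mismatch inside 2.3.19. The registration check can only confirm that a test was done within its window. Contraception is not a test. An investigator's freedom to retest is not a requirement to do so.

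**Conclusion.** The concern holds in a limited form. Under 2.3.8 and 2.3.19 the required pregnancy test may be up to 28 days old at entry, against 3 days for counts and chemistry, and older at first dose by an unstated interval. The readable text therefore does not ensure that an absolute exclusion has been checked recently when treatment begins.

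This rests on three readings: that the 4-week window counts back from entry, that it governs every eligibility study not excepted, and that the Appendix 2 grid does not schedule a later test. If that grid does contain a test at or just before first dose, the gap is closed in practice, and only 2.3.19 needs to be aligned with it.

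The size is bounded. Only women of child-bearing potential are affected. Their share of the planned total, up to 38 patients in 5.4.5, is not given, so no expected number can be calculated. The change is worth making because the safety question is real and the remedy is very cheap. It does not put the trial's statistical conclusions in doubt.

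**What to change.** 1. In 2.3.19, add the serum pregnancy test, for women of child-bearing potential, to the tests repeated on blood already drawn shortly before treatment, and require a negative result before the first dose. The pre-entry repeat draw would serve if dosing follows directly; otherwise the cycle 1 day 1 draw in Appendix 1 would. Tying the repeat to study entry alone would leave the interval from entry to dosing uncovered.
2. Add a pregnancy-test row to the schedule, after checking whether the Appendix 2 grid already has one.
3. Reconcile the post-therapy contraception periods in 2.1.13 and 10.1.6. Which period is right is for the sponsor and the investigator to decide.

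The cost is one extra assay for each woman concerned, on a blood draw that already takes place, and a few lines in an amendment. If the day 1 draw is used, the first infusion has to wait for the result. Nothing changes in the sample size, the decision rules or the analysis.

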## **2.4 Patient Registration**

All patients must be registered on study before beginning therapy. To register a patient for the study, contact [name] [contact]), [name] [contact]), [name] [contact]) or one of the other Associate Investigators.

Authorized staff must register an eligible candidate with NCI Central Registration Office (CRO) within 24 hours of signing consent. A registration Eligibility Checklist from the web site (<http://camp.nci.nih.gov/ccr/welcome.htm>) must be completed and faxed to [contact]. After confirmation of eligibility at Central Registration Office, CRO staff will call pharmacy to advise them of the acceptance of the patient on the protocol prior to the release of any investigational agents. Verification of Registration will be forwarded electronically via e-mail to the research team. A recorder is available during non-working hours.

## **3 STUDY IMPLEMENTATION**

### **3.1 Study Design**

Patients with the chronic, lymphomatous and acute forms of ATL will be treated with 9 or 18 mcg/kg/d for five days of Denileukin diftitox, on an every two week schedule. Nine patients will be treated initially with a dose of 9 mcg/kg/d with expansion to 29 patients if a response is seen in one of the nine initial patients treated. If no response is seen at this dose level, and if no excessive toxicity is seen, an additional 9 patients will be treated at a dose of 18 mcg/kg/d. If a response is seen, this dose level cohort will be expanded to 29 patients. Tumor response will be evaluated after the initial two cycles of treatment. If patients are stable or responding, they will continue treatment with evaluations after every four cycles of treatment for a period of 12 months in total. If patients have achieved a complete remission they shall be treated with a further two cycles of consolidation therapy.

The study will be conducted in accordance with the procedures established by CBER and FDA

### **3.2 Drug Administration**

Denileukin diftitox is for intravenous (IV) use only. Treatment of patients may be administered either on an inpatient or outpatient basis. Patients receiving denileukin diftitox at either 9 or 18 mcg/kg/day for 5 days will receive their first cycle as an inpatient, but if toxicities are acceptable, subsequent dosing may be administered as an outpatient. The daily dose is to be infused over 60 minutes.

Patient's baseline weight will be used to determine all doses of Denileukin diftitox®. Dosing will be adjusted if there is a  $\pm$  10% change in weight.

Patients will be premedicated with acetaminophen (650 mg po) and diphenhydramine (25-50 mg po), 30-90 minutes prior to each infusion and PRN for symptoms. Meperidine (25-50 mg IV) may be given if chills or rigors develop.

Patients will be monitored with vital signs (temperature, pulse, respiration and blood pressure) before and every 15 minutes during the Denileukin diftitox infusion, and then every 30 minutes for a total of 2 hours after the infusion.

Some patients may develop tumor lysis syndrome. If the patient is considered at risk for tumor lysis syndrome; allopurinol, hydration and alkalinsiation will be administered according to the discretion of the Principal Investigator.

The most common side effects observed are elevated transaminases, hypoalbuminemia, vascular leak syndrome, fatigue and flu-like symptoms. These side effects tend to occur less frequently with further cycles.

If infusional adverse reactions occur, the infusion should be discontinued or the rate should be reduced depending on the severity of the reaction (see Section 4.1). Denileukin diftitox dose may be modified at the discretion of the principal investigator. If the patient is unable to tolerate the 9mcg/kg/day dose it may be reduced to 4.5mcg/kg/day. If the patient is unable to tolerate the 18 mcg/kg/day dose it may be reduced to 9 mcg/kg/d. Allergic reactions to dose administration are possible, therefore appropriate drugs and medical equipment to treat acute anaphylactic reactions must be immediately available and study personnel must be trained to recognize and treat anaphylaxis. If symptom of moderate (grade 2) or severe (grade 3) hypersensitivity persist for longer than 6 hours despite treatment of symptoms, further treatment with Denileukin diftitox should be discontinued. If anaphylaxis occurs at any time, further treatment with Denileukin diftitox must be discontinued.

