### 3.3 Treatment Modifications

Dose limiting toxicities are defined as toxicities attributed to study drug administration requiring discontinuation of drug. These consist of:

- Any episode of life threatening Denileukin Diftitox hypersensitivity.
- Any grade III or IV toxicity not easily reversible to grade 1 by standard supportive measures.

In those cases where a toxicity occurs, which is deemed related to the study drug by the Principal Investigator, additional dosing may occur once the toxicity has resolved by 2 grades or to grade 1. The daily dose may be reduced to 4.5mcg/kg/day, for patients in the 9 mcg/kg/d group, or to 9 mcg/kg/d for patients in the 18 mcg/kg/d group.

Patients with life threatening hypersensitivity reactions or grade III or IV toxicity that does not resolve to grade 1, will be taken off treatment but remain on study for follow-up evaluation.

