#### **3.10.2 Any episode of life threatening Denileukin diftitox related hypersensitivity**

- 3.10.3 Any grade III or IV toxicity not easily reversible by standard supportive measures If judged by the PI to be in the best interest of the patient.

**All patients who enter the study and discontinue their treatment early, regardless of the reason for stopping protocol treatment, will if at all possible, have a post treatment evaluation one month after the last dose of Denileukin diftitox as outlined in Section 3.12.**

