## 4 SUPPORTIVE CARE

### 4.1 Acute Hypersensitivity

Acute hypersensitivity reactions to denileukin diftitox should be managed as outlined below. Resuscitative drugs and equipment should be readily available during administration. The dose may be reduced at the discretion of the Principal investigator.

For mild symptoms: (Localized cutaneous reactions such as mild pruritis, flushing, or rash.) Decrease the rate of infusion until recovery from symptoms, and monitor patient; complete denileukin diftitox infusion at the initial planned rate. Diphenhydramine 50 mg, may be administered at the discretion of the treating physician.

For moderate symptoms: (Any symptom not listed above (mild symptoms) or below (severe symptoms) such as generalized pruritis, flushing, rash, dyspnea, or hypotension with systolic BP >80 mmHg.) Interrupt denileukin diftitox infusion, administer diphenhydramine 50 mg i.v., and monitor patient until resolution of symptoms. Resume denileukin diftitox infusion after recovery of symptoms. At the discretion of the treating physician, denileukin diftitox infusion may be resumed at one half the initial infusion rate, then increased incrementally to the initial infusion rate. If symptoms develop after resumption of the infusion, at the discretion of the treating physician, additional oral or i.v. antihistamine may be administered. If resolution of symptoms occurs the infusion may be resumed.

For Severe Symptoms (2% of patients): Systolic blood pressure < 80 mmHg, tachycardia, chest pain or tightness, allergic reaction or anaphylaxis. Interrupt denileukin diftitox infusion, administer diphenhydramine 50 mg i.v., and monitor patient until resolution of

symptoms. If anaphylaxis or severe allergic reaction occurs, treat with corticosteroids or epinephrine, as appropriate. The infusion should be discontinued. Treatment with additional denileukin diftotox may be considered at the discretion of the Principal Investigator with steroid pre-medication in those patients whom have shown evidence of disease response.

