#### Main Adverse Events:

**Acute Hypersensitivity-type Reactions:** were reported in 98 of 143 patients (69%) during or within 24 hours of denileukin diftitox infusion; approximately half of the events occurred on the first day of dosing regardless of the treatment cycle. The constellation of symptoms included one or more of the following, defined as the incidence (%) in these 98 patients: hypotension (50%), back pain (30%), dyspnea (28%), vasodilatation (28%), rash (25%), chest pain or tightness (24%), tachycardia (12%), dysphagia or laryngismus (5%), syncope (3%), allergic reaction (1%) or anaphylaxis (1%). These events were severe in 2% of patients.

**Vascular Leak Syndrome** - This syndrome, characterized by 2 or more of the following 3 symptoms (hypotension, edema, hypoalbuminemia) was reported in 27% (38/143) of patients in the clinical studies. The onset of symptoms in patients with vascular leak syndrome was delayed, usually occurring within the first two weeks of infusion and may

persist or worsen after the cessation of denileukin diftitox. Special caution should be taken in patients with preexisting cardiovascular disease. Weight, edema, blood pressure and serum albumin levels should be carefully monitored on an outpatient basis. This syndrome is usually self-limited and treatment should be used only if clinically indicated.

**Infectious Complications:** Infections of various types were reported by 48% (69/143) of the study population, of which 23% (16/69) were considered severe although these patients had leukemia and were unusually susceptible to infections. Decreased lymphocyte counts (<900 cells/L) occurred in 34% of lymphoma patients. In general, lymphocyte counts dropped during dosing period (Days 1 to 5) and then returned to normal by Day 15. Smaller changes and more rapid recoveries were observed with subsequent courses.

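### Three safety rules disagree within the protocol: re-treatment after anaphylaxis, redosing after grade 4 toxicity that settles at grade 2, and the length of contraception

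*Combined protocol and SAP*

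**What the plan says.** **Anaphylaxis.** Section 3.2 (Drug Administration) states: "If anaphylaxis occurs at any time, further treatment with Denileukin diftitox must be discontinued". Section 3.10.2 lists as an off-treatment criterion "Any episode of life threatening Denileukin diftitox related hypersensitivity", and section 3.3 likewise takes patients with life-threatening hypersensitivity off treatment. Section 4.1 (Acute Hypersensitivity) places anaphylaxis in its severe category and gives its management: "If anaphylaxis or severe allergic reaction occurs, treat with corticosteroids or epinephrine, as appropriate". It stops the infusion, and then says that additional treatment "may be considered at the discretion of the Principal Investigator with steroid pre-medication in those patients whom have shown evidence of disease response".

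**Redosing after toxicity.** For toxicity judged related to the drug, section 3.3 says "additional dosing may occur once the toxicity has resolved by 2 grades or to grade 1". The next paragraph of 3.3 says that patients with "grade III or IV toxicity that does not resolve to grade 1, will be taken off treatment". Section 3.10.3 gives the corresponding stop rule as "Any grade III or IV toxicity not easily reversible by standard supportive measures", without the grade 1 threshold.

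**Contraception.** Inclusion criterion 2.1.13 requires contraception during the trial and for three months after therapy. The cautions in section 10.1.6 advise at least six months for women of child-bearing age and fertile men, because the effects on embryogenesis, reproduction and spermatogenesis are unknown.

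**The concern.** The protocol states no order of precedence among these sections. A clinician managing a severe reaction will probably turn to 4.1, because 3.2 points there. Read alone, 4.1 lets a responder be re-challenged after anaphylaxis. Section 3.3 can be read as allowing another dose at grade 2 after a grade 4 event. A patient who meets only the eligibility requirement stops contraception three months before the period that the drug section advises.

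The 4.1 discretion belongs to the Principal Investigator, who under section 7 also monitors the trial without a data and safety monitoring board. The written rule is therefore the main safeguard. At stake is harm to individual patients, possibly fatal or fetal. The two-stage design and the response analysis are unaffected.

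**Working it through.** The plan gives no figure of its own to reproduce on this point. The check compares the rules and then estimates how many patients they could touch.

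**1. Anaphylaxis rules compared**

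| Section | Trigger | Action |
|---|---|---|
| 3.2 | Anaphylaxis at any time | Mandatory stop |
| 3.3, 3.10.2 | Life-threatening hypersensitivity | Off treatment |
| 4.1 | Severe symptoms, anaphylaxis included | Stop the infusion; more drug possible in responders, with steroids |

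Stopping the infusion in 4.1 cannot mean ending therapy, because the next sentence contemplates more drug. The conflict is confined to responders with anaphylaxis.

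**2. Redosing rules by starting grade (section 3.3)**

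- Grade 2: 2 − 2 = 0, already below grade 1. No conflict.
- Grade 3: 3 − 2 = 1. The two-grade branch and the grade 1 branch coincide. No conflict.
- Grade 4: 4 − 2 = 2. The first rule allows redosing; the second takes the patient off treatment because grade 1 is not reached. Conflict.

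The two-grade branch permits something beyond the grade 1 branch only for a grade 4 event that settles at grade 2, and that is the case the next paragraph forbids.

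**3. Contraception**

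6 − 3 = 3 months' difference. Six months satisfies both statements.

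**4. Expected anaphylaxis cases**

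Inputs from section 10.1.6: 98 of 143 patients had acute hypersensitivity-type reactions, and 1% of those 98 had anaphylaxis.

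- Count: 0.01 × 98 = 0.98, about 1 patient.
- Rate per treated patient: 1/143 = 0.70% (exact 95% CI 0.018% to 3.83%).
- Expected in 29: 29/143 = 0.20 (0.005 to 1.11 over that interval).
- Chance of at least one in 29: 1 − (142/143)^29 = 0.184.
- Also a responder, assuming independence: 0.203 × 0.30 = 0.061 at the target response rate; 0.203 × 0.05 = 0.010 at the null rate.
- If the 18 mcg/kg/d cohort stops at nine: 9/143 = 0.063 expected; 1 − (142/143)^9 = 0.061 chance of at least one.

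**5. Grade 4 events**

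Appendix 5 shows one grade 4 entry, a neutropenia, in nine patients at 9 mcg/kg/d.

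- Rate: 1/9 = 11.1% (exact 95% CI 0.28% to 48.2%).
- In 29 patients: 29 × 1/9 = 3.2 (0.08 to 14.0).

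The documents do not say how many grade 4 events would settle at grade 2. The number caught between the two rules is some unknown part of these events: anywhere from none to about 3 at the observed rate, which is itself very uncertain.

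**The case against.** The strongest reply is that the rules can be read together. Section 3.2 is specific and mandatory. The 4.1 sentence is permissive and covers a broad category that also includes low blood pressure, tachycardia and chest pain, so re-treatment could be read as reserved for those reactions. Likewise, in 3.3 a general permission is followed by a mandatory limit that matches the definition of dose-limiting toxicity at the head of that section. The six-month contraception text is counselling advice in a drug-information section, and the consent form, which may already say six months, is not available here.

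The specific-over-general reading does not rescue 4.1. That paragraph names anaphylaxis twice, gives its treatment, and makes no exception when it turns to re-treatment. For 3.3, taking the stricter sentence as controlling is sensible, but it leaves the two-grade branch with no function in the only case where it matters. Section 3.10.3 does not settle the question: it omits the threshold, and it is followed by words on the investigator's judgement that may be a qualifier or a separate item run together in the extracted text. The contraception reply largely stands, and that item is the weakest of the three.

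Some cautions on size also stand:

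- Twenty-nine is the full cohort. The 9 mcg/kg/d stage ended without a response, and the 18 mcg/kg/d cohort stays at nine unless someone responds. Twenty-nine is still the relevant size for the responder exception, because a response triggers expansion.
- Formal response is first assessed after two cycles, so earlier reactions would usually precede the 4.1 option. Independence ignores this.
- Appendix 5 gives no attribution, whereas the redosing rule covers only related toxicity. Its data come from half the dose now planned.
- Section 10 refers to a single patient on study under Amendment G, so remaining exposure may be well below 29.

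**Conclusion.** The concern holds. The anaphylaxis rules conflict directly for responders, the redosing rules conflict for grade 4 events that settle at grade 2, and the contraception periods differ by three months.

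The likely number affected is small: 0.20 expected anaphylaxis cases in a full cohort of 29, of which 0.01 to 0.06 would be in responders, and at most about 3 grade 4 events at the observed rate. The contraception difference covers every fertile patient. These figures assume that the section 10.1.6 and Appendix 5 rates carry over to 18 mcg/kg/d every 14 days. That may not be so, since the dose is double that behind Appendix 5 and the approved cycle is 21 days. The responder figures also assume that anaphylaxis and response are independent.

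The text should be corrected because the possible harm is serious and the correction is simple, not because many patients are expected to be affected.

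**What to change.** Subject to the sponsor's clinicians, keep the stricter rule already in the protocol in each case:

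1. **Section 4.1:** add to the re-treatment sentence: *except after anaphylaxis or life-threatening hypersensitivity, when treatment is permanently discontinued*.
2. **Section 3.3:** require grade III or IV toxicity to resolve to grade 1 before any further dose. Put the same grade 1 wording in **section 3.10.3**.
3. **Section 2.1.13:** change the period to at least six months after therapy, and check that the consent text agrees.

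The cost is a wording amendment to four sections and a check of the consent form, with no change to sample size, visits or analysis.
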